**Table 9.2.2 Design operating characteristics under different scenarios for the true probability of  $P_d$**

True Value of $P_d$	Probability to Stop	Expected N	Expected N given that we Stopped
0.10	0.003	9.99	6.32
0.30	0.17	9.55	7.38
0.50	0.64	8.01	6.90
0.60	0.84	6.92	6.35

**Table 9.2.3 Stopping rules based on seven interim looks**

Number of Patients	Number to Continue	Probability to Stop	Cumulative Probability to Stop
3	2	0.008	0.008
6	3	0.013	0.021
9	4	0.010	0.031
12	5	0.007	0.038
15	6	0.005	0.044
18	7	0.004	0.047
20	8	0.009	0.048

**Table 9.2.4 Design operating characteristics under different scenarios for the true probability of  $P_d$  for TNBC cohort**

True Value of $P_d$	Probability to Stop	Expected N	Expected N given that we Stopped
0.10	0.003	19.96	6.48
0.30	0.233	17.76	10.38
0.50	0.834	11.01	9.28
0.60	0.967	8.11	7.70

The co-primary efficacy endpoint will be change in TILs. TILs will be assessed in paraffin embedded samples after the study is completed and will have no bearing on impact on continued enrollment for the trial. For each cohort, the mean percent change in TIL score before treatment and after pembrolizumab alone  $\mu_1$  will be compared to the mean change in TIL score before treatment and after pembrolizumab plus radiation  $\mu_2$  using the paired t-test or Wilcoxon sign test depending on the distribution of the data. A significance of 0.05 will be used to declare statistical significance. Let  $SD(\text{diff})$  be the standard deviation of the difference in percent change in TIL score before treatment and after pembrolizumab and before and after treatment with pembrolizumab and radiation. Data from 8 evaluable patients in the HR+ cohort achieve 80% power to detect an effect size of 1.16 using a two-sided paired t-test at the 0.05 level of significance. The effect size is defined as the difference between the two means divided by  $SD(\text{diff})$ ,  $(\mu_1 - \mu_2) / SD(\text{diff})$ . This is equivalent to an absolute difference of 20% between the mean change in TIL scores assuming an  $SD(\text{diff})$  of 17%. For the TNBC cohort, assuming 16 patients are evaluable, the effect size that is detectable with the same power and type I error is 0.75.

Comparisons of clinical characteristics among cohorts will be conducted using descriptive summary statistics using median and range. Changes in TIL score will be compared between cohorts using Fishers exact test.

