## STUDY SCHEMA

This is a prospective, phase Ib/II study of the preoperative combination of pembrolizumab (pembro) and radiation therapy (RT) in patients with operable breast cancer. Patients with newly diagnosed, Stage I-III breast cancer who are planned for breast-conserving surgery and adjuvant whole breast radiation therapy will be recruited into one of 2 cohorts as per their biomarker profile as depicted below. The TNBC cohort will have 50 subjects (10 TNBC subjects for phase Ib and 40 TNBC subjects for phase II) and the HR+ cohort will have 10 subjects. Enrollment will start with the phase Ib TNBC cohort. The trial will be conducted in a Bayesian design, wherein safety as assessed by lack of delay in standard of care treatment will be assessed after 3, 6, and 9 patients have initiated standard of care treatment in each cohort. Standard of care treatment is defined as breast-conserving surgery or initiation of neoadjuvant systemic chemotherapy. If the phase Ib TNBC trial meets a pre-specified safety endpoint, enrollment in

the phase II TNBC trial and HR+ cohort will take place.

Study treatment will consist of 2 doses of neoadjuvant pembro. The second dose will be given in combination with a RT boost. The primary objectives are: 1) to assess the feasibility of the preoperative combination of pembro and RT as defined by the number of patients who do not necessitate a delay in standard of care treatment, 2) to assess the change in tumor infiltrating lymphocyte (TIL) score with therapy. The secondary objectives are to describe the toxicity with preoperative pembro and RT up to 15 weeks after administration of pembrolizumab, to assess the invasive disease-free (iDFS) survival, and to assess the pathological complete response (pCR) rates.

- The first dose of pembro will be given on cycle 1, day 1 (C1D1). Each cycle will be 21 days. The second of pembro dose will be given on C2D1 (+/- 3 days).
- RT will be administered concurrently within one week of the second dose of pembro (C2D1 + 5 calendar days). 8Gy will be delivered in 3 fractions over 3 to 5 business days (for a total dose of 24Gy).
- Standard of care treatment, including breast-conserving surgery or additional neoadjuvant systemic therapy, will be pre-set to start 8 weeks after study enrollment (+/- 5 days).
- Research blood and stool will be obtained after consent up to C1D1. It will also be obtained on C2D1 (+/- 3 days) and at the time of initiation of standard of care treatment (+/- 5 days).

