### 3.0 STUDY DESIGN

#### ***Study Design***

This is a prospective, single-institution, Phase Ib/II study of the preoperative combination of pembrolizumab (pembro) and radiation therapy (RT) in patients with operable breast cancer (TNBC). The two cohorts will consist of 50 TNBC and 10 HR+ women each. Enrollment will start with the Phase Ib TNBC safety cohort. The trial will be conducted in a Bayesian design, wherein safety as assessed by lack of delay in standard of care treatment will be assessed after 3, 6, and 10 patients have initiated standard of care treatment. If at least 80% of the first 10 subjects in the TNBC cohort proceed with standard of care therapy without delay, the combination will be deemed safe in the cohort, and enrollment in the HR+ cohort, as well as continued enrollment in the TNBC cohort (40 subjects), will occur at that time.

Each cohort will be evaluated for delay in curative-intent standard of care treatment every time 3 patients complete study therapy and undergo standard of care treatment. At each of those timepoints, if the posterior probability that a patient experiences a delay in standard of care treatment exceeds 20%, the cohort will stop enrollment. In Bayesian statistics, the posterior probability of a random event or an uncertain proposition is the conditional probability that is assigned after the relevant evidence or background is taken into account. This design will assure that a cohort does not continue enrollment if early delays in standard of care treatment are seen. Enrollment will be carried out continuously and will not be stopped in order to evaluate the posterior probability of a delay. However, the number of patients undergoing assessment for a possible delay simultaneously will not exceed four in each of the 2 cohorts.

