importance of other standard of care therapy, including neoadjuvant systemic therapy in TNBC tumors. Therefore, the standard of care curative-intent treatment will be set to start 8 weeks (+/- 5 days) after trial initiation, and the primary endpoint is to assess delays in this pre-planned date.

Bleicher, et al reported increased breast cancer-specific mortality with delays from time of diagnosis to surgery of > 60 days in a retrospective cohort analysis from the SEER Medicare database. This was particularly true in Stage I patients. In a similar retrospective analysis from the California Cancer Registry, Chavez-Macgregor, et al reported worse overall survival and breast cancer-specific survival in patients whose adjuvant chemotherapy was delayed beyond 90 days after surgery. The planned standard of care treatments in this study are within the timeframes of these analysis. The Bayesian design of the trial will prevent ongoing recruitment into each of the cohorts if the probability of surgical delays exceeds pre-specified limits after 3, 6, and 9 patients undergo standard of care treatment in each cohort.

This study requires tumor samples collected at 3 different time points for each patient to complete the immune correlative analysis. Therefore, a minimum tumor size of 2 cm was chosen to maximize the probability of having sufficient tumor tissue available for analysis.

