## 9.2 Data Sets Analyzed

### Data Analyses/Study Endpoints

#### 9.2.1 Efficacy Analysis

The primary analysis will be based on an intention-to-treat approach and will include all subjects who receive a dose of study drug.

Phase Ib:

The primary efficacy endpoint will be feasibility as defined by the number of patients who do not necessitate a delay in standard of care treatment. Let  $P_d$  be the true probability that a patient experiences a delay. The trial will stop if there is statistical evidence that  $P_d$  exceeds 20%. We will use a Bayesian sequential design by checking whether  $P_d$  exceeds this threshold value after 3, 6, 9, ... patients are evaluable for feasibility. The decision rule is to stop the trial if the posterior probability that  $P_d$  exceeds 0.20 is 0.95 or more;  $P(P_d > 0.2 | \text{data}) > 0.95$ . A non-informative prior distribution for  $P_d$  will be used. Table 9.2.1 gives the stopping rules for the design at each look and column 2 gives the maximum number of patients with delay in order for the trial to proceed. Stopping rules will also apply for any patients with clinical progression of disease during study treatment, although this is expected to be uncommon. For example, if 4 or more delays in treatment are observed after enrolling 6 patients, the trial stops. The third column gives the probability of stopping the trial when in fact, the true  $P_d = 0.20$ . This is the equivalent of the Bayesian type I error probability. The target type I error probability was set at 0.05.

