**Table 9.2.1 Stopping rules based on four interim looks**

Number of Patients	Number to Continue	Probability to Stop	Cumulative Probability to Stop
3	2	0.008	0.008
6	3	0.013	0.021
9	4	0.010	0.031
10	4	0.011	0.042

Number to continue is the maximum number of delays in standard of care treatment for not stopping the trial.

Table 9.2.2 gives the design operating characteristics under selected values of the true probability  $P_d$  for the HR+ cohort. It gives the probability of stopping the trial under the alternative hypothesis, the expected sample size, and the average sample size given that the trial stopped. For example, if the true value of  $P_d$  is 0.5, then there is an 64% chance that the trial is stopped early and the average sample size is about 8. On the other hand, there is a small chance of stopping the trial if  $P_d$  is small; 0.3% chance of stopping the trial when in fact  $P_d = 0.1$ . Tables 9.2.3 and 9.2.4 list the same operating characteristics for the TNBC cohort.

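### The TNBC delay-stopping tables are calculated for at most 20 patients, but the TNBC cohort is 50, so the stated error and stopping probabilities do not describe the current design

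*Combined protocol and SAP*

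**What the plan says.** The Study Schema gives the cohort size: "The TNBC cohort will have 50 subjects (10 TNBC subjects for phase Ib and 40 TNBC subjects for phase II". Section 3.0 repeats it: "The two cohorts will consist of 50 TNBC and 10 HR+ women each".

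Section 9.2.1, under a Phase Ib heading, gives the rule: "The trial will stop if there is statistical evidence that" the true delay probability Pd is above 0.20, meaning a posterior probability of at least 0.95. The prior is called non-informative, without parameters, and the target type I error is 0.05. The same section says "Tables 9.2.3 and 9.2.4 list the same operating characteristics for the TNBC cohort". Table 9.2.3 ("Stopping rules based on seven interim looks") has looks at 3, 6, 9, 12, 15, 18 and 20 patients, with at most 2, 3, 4, 5, 6, 7 and 8 delays allowed for continuing.

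The look schedule differs by place:

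- Study Schema: 3, 6 and 9 patients in each cohort.
- Section 3.0, Study Design: 3, 6 and 10 patients, and also "Each cohort will be evaluated for delay in curative-intent standard of care treatment every time 3 patients complete study therapy".
- Section 3.0, Study Population: "after 3, 6, and 9 patients undergo standard of care treatment in each cohort".
- Section 9.2.1: 3, 6, 9 and onward with no stated end.

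Sections 3.0 and 9.1 add a separate criterion: at least 80% of the first 10 TNBC patients must proceed without delay before enrolment goes on.

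**The concern.** Twenty patients is neither the Phase Ib group (10) nor the whole TNBC cohort (50). The amendment log mentions a former TNBC size of 20, which probably explains where the tables come from, but the conflict lies within the current text.

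Feasibility, defined by absence of delay, is a primary objective, and Section 3.0 relies on this design to halt a cohort in which curative-intent treatment is being delayed. A monitoring committee using the plan has no printed limit after patient 20. It also cannot derive one with confidence, because the prior is missing. The error rate and expected sample sizes that justify the design belong to a different maximum sample size.

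**Working it through.** **Method.** Let c_j be the largest number of delays allowed at look j, and m_j the number of new patients since the previous look. The probability of being open with x delays at look j is

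f_j(x) = Σ over k ≤ c_(j−1) of f_(j−1)(k) · C(m_j, x−k) · Pd^(x−k) · (1−Pd)^(m_j−x+k).

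The stop probability at look j is the sum of f_j(x) over x > c_j.

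**1. Reproducing the plan.** With Table 9.2.3's looks and limits at Pd = 0.20, the first look is 0.2³ = 0.008. The successive increments are 0.0080, 0.0131, 0.0101, 0.0073, 0.0053, 0.0039 and 0.0009, for a cumulative 0.0484 (printed 0.048).

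| Pd | P(stop), computed | P(stop), printed | Expected N, computed | Expected N, printed |
|---|---|---|---|---|
| 0.10 | 0.0029 | 0.003 | 19.96 | 19.96 |
| 0.30 | 0.2326 | 0.233 | 17.76 | 17.76 |
| 0.50 | 0.8342 | 0.834 | 11.06 | 11.01 |
| 0.60 | 0.9667 | 0.967 | 8.11 | 8.11 |

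The tables are therefore right, apart from small slips, for a maximum of 20. The last-row increment is 0.0009. The printed 0.009 cannot move the cumulative value from 0.047 to 0.048.

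**2. Expected N with 50 patients.** If the table is used to 20 and nothing follows, expected N at Pd = 0.30 is 17.76 + 30 × (1 − 0.2326) = 40.8. At Pd = 0.50 it is 11.06 + 30 × (1 − 0.8342) = 16.0.

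**3. Does the general rule supply the missing limits?** With a Beta(a, b) prior and x delays in n patients, the posterior is Beta(a + x, b + n − x). Stop if P(Pd > 0.20) exceeds 0.95. The prior is an assumption, so five were tried. The last column applies the rule every 3 patients and at 50, without the 80% criterion.

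| Prior | Max delays at n = 3 | n = 15 | n = 18 | n = 20 | False stop by 50, Pd = 0.20 |
|---|---|---|---|---|---|
| Printed table | 2 | 6 | 7 | 8 | not given |
| Beta(0.2, 0.8) | 2 | 5 | 6 | 7 | 0.14 |
| Beta(0.4, 1.6) | 2 | 6 | 6 | 7 | 0.13 |
| Beta(1, 4) | 2 | 6 | 7 | 7 | 0.11 |
| Beta(0.5, 0.5) | 1 | 5 | 6 | 7 | 0.25 |
| Beta(1, 1) | 1 | 5 | 6 | 6 | 0.26 |

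For example, 2 delays in 3 under Beta(1, 1) gives a posterior probability of 0.973, so the written rule stops where the table continues. None of the five matches the table at 20.

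Two gentler extensions also pass 0.05. Continuing the table's own step (n/3 + 1) to 50 gives 0.060. A stricter 0.99 cutoff with Beta(1.5, 1.5), which does reproduce every printed limit, gives 0.073 when carried to 50.

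**4. Adding the 80% criterion.** At most 2 delays in 10 are allowed, whereas Table 9.2.1 allows 4. At Pd = 0.20, P(3 or more of 10) = 1 − (0.1074 + 0.2684 + 0.3020) = 0.322. Combined with Table 9.2.3, and treating failure of the criterion as stopping:

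- Pd = 0.20: stopped by patient 20 with probability 0.32.
- Pd = 0.30: still open after 20 with probability 0.38.
- Pd = 0.40: still open after 20 with probability 0.16.

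If nothing were checked after 20, the expected further delays would be 0.38 × 30 × 0.30 = 3.4 and 0.16 × 30 × 0.40 = 1.9.

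**The case against.** A reader might infer that patients 21 to 50 have no stopping rule at all. The documents do not support that. Section 3.0 evaluates each cohort every 3 patients without an upper limit, and Section 9.2.1 states an explicit posterior rule with an open-ended sequence of looks. What is missing is a tabulated limit, the operating characteristics and the prior needed to calculate them. Section 10.5.2 also provides a data and safety monitoring committee, and a research monitor with authority to stop the protocol. Enrolment is not unprotected, although such oversight does not replace a defined boundary.

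A reader might also take from Table 9.2.3 alone that the cohort would still be open after 20 patients with probability 0.77 at Pd = 0.30 and 0.45 at Pd = 0.40. Those figures ignore the 80% criterion, which reduces them to 0.38 and 0.16.

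The strongest defence concerns scope. The delay rule sits under Phase Ib, which has 10 TNBC patients, and Phase II has its own two-stage response rule. On that reading Table 9.2.1 covers the monitored patients and the 20-patient tables are leftovers. This is a fair reading, but the reference to each cohort in Section 3.0 points the other way. Even if it is right, Section 9.2.1 still presents 20-patient figures as the TNBC operating characteristics, and 40 patients would then fall outside delay monitoring without the plan saying so.

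**Conclusion.** The point holds on either reading of scope. Tables 9.2.3 and 9.2.4 are correct in substance for 20 patients and describe neither 10 nor 50. The 0.048 false-stop probability, the stop probabilities and the expected sample sizes should not be relied on for the current TNBC cohort.

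The size depends on assumptions. Under the five priors tried, the written 0.95 rule carried to 50 gives a false-stop probability of about 0.11 to 0.26 against the 0.05 target. No single value can be given, because the prior is not stated. The figures of 0.32, 0.38 and 0.16 do not depend on a prior; they rest on the printed limits and on treating failure of the 80% criterion as stopping.

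**What to change.** 1. State whether delay monitoring covers the 10 Phase Ib patients or all 50 TNBC patients, and reconcile the look schedules in the Study Schema, Section 3.0 (Study Design and Study Population) and Section 9.2.1.
2. State the prior's parameters and confirm the posterior cutoff that generates the limits.
3. If monitoring covers 50, replace Tables 9.2.3 and 9.2.4 with limits and operating characteristics to 50, including the 80% criterion at 10. Either calibrate the cutoff to the 0.05 target or state the false-stop probability reached. Because the 80% criterion alone fails with probability 0.322 at Pd = 0.20, the target can apply only to the posterior boundary; report the combined figure beside it.
4. If monitoring is Phase Ib only, delete the 20-patient tables and present the 10-patient table with the 80% criterion included.
5. Correct 0.009 to 0.0009 if the 20-patient table is kept anywhere.

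The cost is a recalculated table and aligned wording. The price in the design is a less favourable stated false-stop figure or slightly wider late limits. No added patients or data collection are needed.

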#### **5.8 Subject Replacement**

Subjects who withdraw from the study treatment prior to starting or during the study intervention and fail to complete the intervention may need to be replaced at the discretion of the study PI. Subjects who complete the study intervention, but are not evaluable for the primary endpoint of tumor infiltrating lymphocytes will also be replaced at the discretion of the study PI.

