#### 6.3.6 Survival Status

Survival status assessment and any documentation of recurrence (if possible) will be conducted every 6 months for up to 5 years following the end of treatment. Study staff will record survival status and recurrence via medical record review, phone call, or at standard clinical visits.

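### TIL samples found unscorable only when the slides are read are found too late for the replacement that Section 5.8 allows; a score-blind adequacy check during accrual would close the gap cheaply

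*Combined protocol and SAP*

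**What the plan says.** Section 5.8 (Subject Replacement) covers patients who complete treatment without a usable TIL result: "Subjects who complete the study intervention, but are not evaluable for the primary endpoint of tumor infiltrating lymphocytes will also be replaced at the discretion". The decision lies with the principal investigator.

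Section 9.2.1 (Efficacy Analysis, Phase Ib), in the text after Table 9.2.4, sets the timing of the TIL work: "TILs will be assessed in paraffin embedded samples after the study is completed and will have no bearing on impact on continued enrollment".

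The same text gives the HR+ power statement: "Data from 8 evaluable patients in the HR+ cohort achieve 80% power to detect an effect size of 1.16". The test behind that figure is specified as "using a two-sided paired t-test at the 0.05 level of significance". The effect size is then translated as "absolute difference of 20% between the mean change in TIL scores assuming an", and the SD of the paired difference is put at 17%. Section 9.1 plans 10 HR+ subjects.

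The documents do not define TIL-evaluable, do not say when replacement closes, and do not provide for checking the Week 4 or Week 7 paraffin samples during accrual. The only sufficiency condition is in footnote 10 of the Time and Events Table (Section 6.4), and it applies to archived baseline tissue in the HR+ cohort.

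**The concern.** A replacement rule works only if the need for replacement is known while patients can still be enrolled. Some failures are obvious at once. Others are not: a core may exist and be embedded, yet turn out to have no scorable tumor stroma when the H&E slide is examined. Under the timing in Section 9.2.1, that examination follows the end of the study.

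The documents make such failures plausible:

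- Section 3.0 requires tumor samples at three time points per patient.
- Section 8.2 gives one paraffin core per time point to TIL scoring, multispectral IHC and two kinds of sequencing together.
- Appendix B excludes necrosis, regressive hyalinization and the earlier biopsy site from scoring, and notes that no method has been validated for scoring TILs after neoadjuvant treatment. Two of the three samples follow treatment, one of them after radiation.

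At stake is the power of the HR+ co-primary comparison, which rests on 8 evaluable patients. There is also a secondary risk. If slides were examined early so that Section 5.8 could work, no written rule would keep the adequacy judgment apart from the TIL score.

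**Working it through.** **Step 1. What is known when**

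| Reason for no TIL result | When it is known | Can Section 5.8 act? |
|---|---|---|
| Withdrawal or incomplete treatment | During accrual | Yes |
| Biopsy not done | During accrual | Yes |
| Insufficient archived baseline tissue (HR+) | At screening | Yes |
| Sample present but unscorable on the slide | At reading, after the study under Section 9.2.1 | No |

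Only the last row is affected.

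**Step 2. The plan's own power figures**

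Inputs from Section 9.2.1: paired t-test, two-sided 0.05; HR+ n = 8, effect size d = 1.16; TNBC n = 16, d = 0.75.

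Formula: power = P(T > c) + P(T < −c). Here T is noncentral t with n − 1 degrees of freedom and noncentrality d√n, and c is the 0.975 quantile of the central t with n − 1 degrees of freedom.

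- HR+: noncentrality 1.16 × √8 = 3.28, power 0.803. The stated 80% is reproduced.
- With the unrounded ratio, d = 20/17 = 1.18, power is 0.813.
- TNBC: noncentrality 0.75 × √16 = 3.00, power 0.801. This is also reproduced.
- Allowance: 10 enrolled against 8 needed leaves 2 patients, or 20%; 8/(1 − 0.20) = 10.

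**Step 3. Power by number evaluable (HR+)**

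| Evaluable n | Power at d = 1.16 | d detectable at 80% power | Difference at SD 17 (points) |
|---|---|---|---|
| 10 | 0.903 | 1.00 | 16.9 |
| 9 | 0.860 | 1.07 | 18.1 |
| 8 | 0.803 | 1.16 | 19.7 |
| 7 | 0.726 | 1.27 | 21.6 |
| 6 | 0.627 | 1.43 | 24.4 |
| 5 | 0.504 | 1.68 | 28.6 |

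**Step 4. How likely a shortfall is**

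The documents give no evaluability rate, so q, the chance that a patient is evaluable, is an assumption shown over a range. No replacement is assumed. With X the number evaluable, X ~ Binomial(10, q), and expected power = Σ P(X = k) × power(k).

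At q = 0.8, P(X = 10) = 0.107, P(X = 9) = 0.268 and P(X = 8) = 0.302. They sum to 0.678, so P(X < 8) = 0.322. Expected power is 0.107 × 0.903 + 0.268 × 0.860 + 0.302 × 0.803 + 0.201 × 0.726 + 0.088 × 0.627 + 0.026 × 0.504 + smaller terms = 0.787.

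| Assumed q | P(fewer than 8 of 10) | Expected power |
|---|---|---|
| 0.9 | 7% | 85% |
| 0.8 | 32% | 79% |
| 0.7 | 62% | 70% |

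**Step 5. TNBC**

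If all 50 planned TNBC patients contribute TIL data, the chance of at least 16 evaluable rounds to 1.0 even at q = 0.6. The point therefore concerns the HR+ cohort.

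**The case against.** The strongest reply is that the two sections do not conflict. The sentence in Section 9.2.1 follows the stopping-rule tables and can be read as saying only that TIL results do not drive stopping. A yes/no look at tissue adequacy is not a TIL assessment, so nothing written forbids one. This stands. A reader might infer that the two rules cannot both be followed, but the text does not go that far. What it lacks is the step that would let them work together.

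A reader might also infer that replacement is impossible or that HR+ power is unprotected. Neither is supported. Most reasons for non-evaluability surface during accrual, and the two-patient allowance absorbs the first two failures. Where surgery is the standard treatment, the Week 7 sample is surgical tissue, not a core. Replacement is also discretionary, so Section 5.8 never guaranteed 8 evaluable patients.

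The assumed rates may be too pessimistic. If q includes failures visible in time, some of those patients could be replaced and the shortfall would be smaller. Even with no replacement, expected power at q = 0.8 is about one point below 80%.

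Two further inferences go beyond the text. One is a delay of years: survival status "will be conducted every 6 months for up to 5 years following the end of treatment" (Section 6.3.6), but the plan does not say whether study completion includes that follow-up, and the gap opens once accrual closes in any case. The other is that the investigator would see scores before deciding on replacement. Section 8.1 assigns scoring to a dedicated breast pathologist, and nothing says the scores are shared. The text simply has no safeguard on this.

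What remains is the unscorable sample found only at reading, for which no check is specified while replacement is still open.

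**Conclusion.** This is a cheap improvement, not an error in the plan's figures, which reproduce. The stated 80% power holds with 8 evaluable HR+ patients and is lost only if 3 or more of 10 cannot be evaluated. The size of the risk depends on an evaluability rate that the documents do not give: slight at 0.9, about an even trade with the built-in allowance at 0.8, and material at 0.7, where expected power is about 10 points below the stated figure. These results assume that patients fail independently at one common rate, that no failures are replaced, that the effect size is 1.16, and that only patients with all needed samples enter the paired test. The matter should be settled before HR+ accrual ends, because lost evaluability cannot be recovered afterwards.

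**What to change.** **Section 9.2.1**

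- Have the study pathologist record a yes/no adequacy result, without a TIL score, as each baseline, Week 4 and Week 7 paraffin sample is processed. Baseline belongs in the check because both percent changes are measured from it.
- Read all TIL scores in one batch after the cohort's last Week 7 sample, in place of the present timing.
- State that TIL scores, as distinct from sample adequacy, have no bearing on enrollment.

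**Section 5.8**

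- Define TIL-evaluable.
- Allow TIL-related replacement only on the adequacy record, only before accrual to the cohort closes, and only for technical failures: no tissue, or an insufficient or unprocessable sample. Accrual should not be declared closed until the last Week 7 adequacy record is in; otherwise late failures are still missed.
- Do not replace a patient whose adequately sampled post-treatment tissue shows no residual invasive tumor. That may be a treatment effect, and replacing such patients would select against response. Report them separately.

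**Cost.** Wording in two sections, and a brief adequacy check by the same pathologist during accrual. One limit remains: patients without residual tumor still reduce the evaluable number, so 8 evaluable is better protected but not guaranteed.

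### The TNBC power statement for the co-primary TIL endpoint is calculated correctly for 16 evaluable patients, but 16 fits no TNBC cohort in the current design

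*Combined protocol and SAP*

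**What the plan says.** Change in TIL score is a primary objective (Section 2.1.2) and the co-primary endpoint (Sections 2.4 and 9.2.1). Within each cohort, the change from baseline after pembrolizumab alone is compared with the change from baseline after pembrolizumab plus radiation, by paired t-test or a Wilcoxon alternative. The text sits under the Phase Ib subheading of Section 9.2.1, after Table 9.2.4.

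- Significance level: "A significance of 0.05 will be used to declare statistical significance".
- HR+ cohort: "Data from 8 evaluable patients in the HR+ cohort achieve 80% power to detect an effect size of 1.16 using a two-sided paired t-test". The plan adds "This is equivalent to an absolute difference of 20% between the mean change in TIL scores", using an SD(diff) of 17%.
- TNBC cohort: "For the TNBC cohort, assuming 16 patients are evaluable, the effect size that is detectable" is 0.75, at the power and significance level used for HR+.

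On cohort size, the Study Schema says "The TNBC cohort will have 50 subjects (10 TNBC subjects for phase Ib and 40 TNBC subjects for phase II", and Section 3.0 says "The two cohorts will consist of 50 TNBC and 10 HR+ women each". Section 9.2.1 does not say whether the TNBC test uses the 10 Phase Ib patients, the 40 Phase II patients or all 50. No TNBC evaluability rate is given anywhere.

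**The concern.** A power statement is useful only if its sample size can arise under the design. Sixteen evaluable patients cannot come from 10. From 40 or 50, it would mean losing well over half of the TIL data, and nothing in the plan anticipates that.

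This is the only stated sensitivity for a co-primary endpoint in the trial's main cohort. As written, a reader cannot tell whether the TNBC comparison will be much weaker or much stronger than stated, because the direction depends on an analysis set that the plan does not define.

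**Working it through.** **Inputs.** Two-sided alpha 0.05, 80% power, paired t-test, HR+ 8 evaluable with effect size 1.16, TNBC 16 evaluable with effect size 0.75, and SD(diff) 17% (all Section 9.2.1). TNBC enrolment is 10 + 40 = 50 (Study Schema, Section 3.0). HR+ enrolment is 10.

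**Formula.** A paired t-test on n differences with standardised effect d has n − 1 degrees of freedom and noncentrality d√n. With c the two-sided 5% critical value of t on n − 1 degrees of freedom, power is P(|T| > c), where T is noncentral t. The detectable effect is the d at which power equals 0.80.

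**Step 1: reproduce the plan's figures.**
- TNBC, n = 16: noncentrality 0.75 × √16 = 3.00, power 80.06%. Solving for 80% gives d = 0.7495. The stated 0.75 reproduces.
- HR+, n = 8: power at 1.16 is 80.3%, and solving for 80% gives d = 1.156. The stated 1.16 reproduces. The stated 20% difference over an SD of 17% is 20/17 = 1.176 (power 81.3%), which agrees apart from rounding.
- Other methods do not give 0.75 at n = 16: the two-sided normal approximation gives 0.700 and a one-sided exact test gives 0.652. The plan therefore used the exact two-sided method.

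**Step 2: compare 16 with the current cohorts.**
- Phase Ib: 16 of 10 is impossible.
- Phase II: 16/40 = 40% evaluable.
- All TNBC: 16/50 = 32% evaluable.
- HR+ implied ratio: 8/10 = 80%. At that ratio, 16 evaluable needs 16/0.80 = 20 enrolled.

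Tables 9.2.3 and 9.2.4 describe a TNBC cohort of 20: the last look is at 20 patients, and the expected sample size at a delay probability of 0.10 is 19.96. Appendix A records an earlier TNBC size of 20 (Amendment 6). That log entry explains where 16 probably came from. The inconsistency itself lies within the current text.

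**Step 3: recompute for cohorts that exist.** The 80% rows carry the HR+ ratio over to TNBC as an assumption, and the 100% rows show the other end of the range. The last column is 17 × d and assumes that the HR+ SD(diff) applies to TNBC.

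| Evaluable n | Basis | Detectable effect, 80% power | Power at 0.75 | Difference if SD(diff) = 17% |
|---|---|---|---|---|
| 8 | 80% of 10 (Phase Ib) | 1.16 | 45% | 19.7% |
| 10 | 100% of 10 | 1.00 | 56% | 16.9% |
| 16 | as stated | 0.75 | 80% | 12.7% |
| 32 | 80% of 40 (Phase II) | 0.51 | 98% | 8.7% |
| 40 | 80% of 50, or all of Phase II | 0.45 | 99.6% | 7.7% |
| 50 | 100% of 50 | 0.40 | 99.9% | 6.9% |

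If the Wilcoxon signed-rank test is used, its asymptotic efficiency of 0.955 raises these effect sizes slightly (for example 1.18 at n = 8 and 0.41 at n = 50). The picture does not change.

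**The case against.** The strongest reply is that the TNBC sentence is conditional on 16 evaluable patients, and under that condition it is true. That stands. A reader might infer that 0.75 is a miscalculation, but the figure reproduces exactly, so the documents do not support that.

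A second reply is that 16 counts evaluable rather than enrolled patients, so a mismatch with enrolment proves nothing alone. There are real reasons for loss: Appendix B excludes necrotic areas and the previous core-biopsy site, and notes that no validated method exists for scoring TILs after neoadjuvant treatment. This stands as a reason not to treat 80% as known for TNBC. It does not rescue 16. For Phase Ib the number is impossible, and for 40 or 50 no passage gives or implies a rate of 40% or 32%. Other provisions point to higher yield: a fresh baseline biopsy is required in TNBC (Section 6.4, footnote 10), the Week 4 biopsy is mandatory (Section 4.1.20), and patients without evaluable TILs are replaced at the investigator's discretion (Section 5.8).

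A third reply is that the test is planned per cohort with scoring after study completion, and the TNBC cohort is 50, so 16 is merely cautious. That reading is open. So is the narrower one: the text falls under Phase Ib, and Section 9.1 says TIL assessment in the Phase Ib cohort will establish immunogenicity. The plan does not settle the matter.

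Finally, TIL results have no effect on continued enrolment, so no stopping or go/no-go decision depends on this figure. That is correct and limits how serious the point is.

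**Conclusion.** The 16-patient statement is an outdated sample-size assumption with a correct calculation attached. It describes a TNBC cohort of about 20 that the current design does not have.

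The direction of the discrepancy is undetermined. If Phase Ib is the analysis set, the stated sensitivity is optimistic: the detectable effect is 1.00 to 1.16 rather than 0.75, and power at 0.75 is 45% to 56%. If all TNBC patients are analysed, it is conservative: 0.40 to 0.45, with power above 99%. A reader might infer that the co-primary endpoint is underpowered, or that a null Phase Ib result will be taken to rule out an effect of 0.75. The first holds in only one of these two branches, and the documents plan no such use of a null result.

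The ranges rest on 80% to 100% evaluability, the lower end borrowed from HR+. Any absolute difference rests on the 17% SD(diff), which the plan states only for HR+. This should be fixed, but it does not threaten the conduct of the trial.

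**What to change.** In Section 9.2.1, state which TNBC patients enter the TIL comparison (Phase Ib only, Phase II only, or all), give the evaluable number expected from that set and its basis, and replace the 16-patient sentence with the matching figure:

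- Phase Ib only: detectable effect size about 1.16 with 8 evaluable, 1.00 with 10.
- Phase II only: about 0.51 with 32 evaluable, 0.45 with 40.
- All TNBC: about 0.45 with 40 evaluable, 0.40 with 50.

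Label the evaluability rate as an assumption. If an absolute difference is quoted, give an SD(diff) for TNBC or say that the HR+ value is being borrowed. Reconcile Tables 9.2.3 and 9.2.4 with the current TNBC cohort in the same amendment, since they share the 20-patient basis.

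For the TIL power statement the cost is a sentence or two, best settled before TILs are analysed. Enrolment, procedures, the test and alpha are unchanged. The only downside is a less favourable stated sensitivity if Phase Ib turns out to be the intended set.
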